### **The rationale for focusing on HAART medication adherence in heavy drinkers**

We have chosen HAART adherence as our primary HIV outcome because it is one of the most proximal steps in the pathway between alcohol consumption and poor HIV outcomes. The association between HAART adherence and HIV treatment outcomes is well-established [72, 73]. However, the optimal level of HAART adherence is not known. Nonetheless, it has been shown that the highest levels of adherence (>95%) are an appropriate goal [74] and if not attainable, incremental increases in adherence at levels < 95% should be considered worthwhile endpoints [75-77]. Therefore, in the current study we are evaluating HAART adherence in terms of the proportion of patients achieving 95% or greater HAART adherence. The threshold of 95% adherence is used because of its consistent association with improved clinical, virological, and immunological outcomes [74]. Although one could argue that lesser levels of adherence might produce a satisfactory viral load response, particularly with certain types of HAART regimens (e.g., non-nucleoside reverse transcriptase inhibitor-based regimens) [29], 95% remains a standard target for HAART adherence and is therefore the most compelling choice for a primary adherence measure. Furthermore, lower adherence levels (e.g. 80%), while potentially resulting in adequate viral load suppression, run the risk of increasing the danger of accumulating HIV resistance mutations and decreasing future treatment options. Indeed, studies have suggested that the maximum rate of accruing resistance mutations accrues in the range of 70-80% [78, 79]. This finding reinforces our rationale for choosing greater than 95% HAART adherence as the primary outcome measure.

In the context of alcohol use, one study found that in HIV-infected patients, there was no difference in biological markers between non-drinking and drinking patients receiving HAART [1]. A second study showed that in HIV-infected patients, there was no difference in biological markers in all drinking groups not on HAART, but drinkers on HAART had worse markers than drinkers not on HAART [5]. Possible explanations include the effect of alcohol on the immune system, alcohol-related liver toxicity, drug interactions between alcohol and HAART medications, and the behavioral effects of alcohol on HAART adherence. While there may be several pathways in which NTX may improve HIV outcomes (Figure 1) the other HIV outcome data we are collecting for each step of these pathways will inform the potential contribution of each step.

**Figure 1.** Pathways of how VIVITROL may lead to improved HIV outcomes

**Pharmacy refill provides an accurate measure of HAART adherence and refill “persistence” is valid, reliable, and linked to clinical outcomes in HIV**

Measuring HAART adherence can be challenging and can include self-report, pill count, and electronic monitoring. One additional assessment of adherence that is amenable to measurement, and will be used in the current trial, is “persistence”. Persistence is defined as the continuous refill of prescribed medications using pharmacy data. Persistence can be conceptualized as necessary, though not sufficient, for adherence to occur. Without the filling and refilling of medications, patients can not adhere to their medications. Unlike other adherence measurements such as self-report, pill count, or electronic monitoring, persistence is an objective measure that does not rely on provider or patient action to obtain. It can also be updated easily so as to avoid the pitfall of defining an individual as adherent at a single point in time and miss their later non-adherence [75]. Persistence has been used to measure patients’ adherence to HAART [80], to NTX for alcohol treatment [81] and to investigate refill behaviors with drug regimens such as statins and anti-hypertensive medications used for other chronic diseases [82, 83]. There are a number of ways that pharmacy refill data can be analyzed to create persistence measures of adherence. The medication possession ratio (MPR) is a commonly used metric that has been validated with virologic response [84-86]. It is calculated as the days’ supply of medication divided by the number of days between the first fill and the last refill and represents the maximum possible adherence that a patient can attain over a defined refill period. The MPR has the capacity to detect inconsistent adherence patterns, is low-cost and has been validated [87]. Within HIV, pharmacy refill of HAART has been used to characterize the following associations: CD4 levels and HAART initiation [88], intermittent use of HAART and mortality [72], as well as HAART adherence and virologic response [89].

**The rationale for using Medical Management (MM) and HAART Medication Coaching (MC) counseling in conjunction with NTX**

The role of counseling is well-established in the care of patients with alcohol problems. MM is a largely medical approach to counseling which is appealing because of its familiarity to practitioners and ease of implementation in a setting that does not routinely provide addiction treatment (e.g. HIV clinic). This type of approach is consistent with studies evaluating psychoeducational counseling in patients with diabetes, hypertension, asthma or congestive heart failure suggesting that intensive education about a patients medical condition and advice about disease management improves treatment effectiveness [90-98].

HIV primary care clinics often provide onsite care for comorbid medical conditions including psychiatric conditions, HCV, and most recently opioid dependence with buprenorphine [99]. Onsite treatment of alcohol use disorders in patients with HIV would allow for integrated care for both disorders. Our earlier work in primary care compared NTX combined with “primary care management” versus NTX combined with cognitive behavior therapy and found similar results between the two treatments during the initial 10 weeks of treatment [57]. The feasibility and efficacy of combining MM with NTX was also documented in the COMBINE Study [10]. For the proposed study we will provide MM along with counseling, termed Medication Coaching (MC) [11], designed to enhance HAART medication adherence in HIV-infected individuals with substance use disorders. We have used an earlier version of MC as an adjunct to drug counseling in HIV-infected opioid dependent patients receiving buprenorphine in an HIV clinic [100, 101].

**Medical concerns of NTX treatment in HIV-infected individuals**

***Increased prevalence of hepatitis C (HCV)***

Because of its potential for hepatotoxicity, NTX should be used with caution in individuals with impaired hepatic function. We plan to use low, but effective doses of NTX, and to assess hepatic safety using a standard self report form [102] and serial serum transaminases in the proposed study. Approximately 30% of HIV-infected individuals in the U.S. are co-infected with HCV [103]. HIV has a significant effect on the progression of HCV to severe liver disease [104-106]. After 15 years of infection with HCV, those co-infected with HIV have a 25% risk of cirrhosis, while those with HCV alone have only a 6.5% risk [105]. Co-infection may increase the risk but not the severity of hepatotoxicity from HAART medication, and therefore HAART should not be avoided in these individuals, but transaminases need careful monitoring [103, 107, 108]. VIVITROL can also have hepatotoxic effects, though at higher dosages than will be used in the proposed study. A recent large study of extended release VIVITROL found that mean liver enzymes did not change significantly over the course of treatment and there was no effect of medication on the proportion of patients in the different groups who had liver enzyme elevations higher than several times the upper limit of normal [61]. In addition, it has been found to be safe for use in patients with mild to moderate liver impairment [109] with evidence of a 15% greater reduction in liver enzyme levels in the VIVITROL group as compared with the placebo group [110]. VIVITROL is approved for use in patients who meet criteria for Child-Pugh classification A and B indicating tolerance in patients with impaired hepatic function. While these data are reassuring, monitoring of liver function, to assess for hepatotoxicity, will be important, especially in HIV/HCV co-infected patients.

***Lower tolerance for medication interactions and side effects (NTX and HAART)***

While there is little literature on interactions between NTX and HAART, based on previous studies outlining metabolism of NTX, these interactions appear to be minimal. The majority of HAART medications are metabolized via the CYP450 system. This metabolic pathway is known to lead to drug interactions with a number of medication classes. NTX,

however, is not completely metabolized via CYP450 and therefore significant interactions are not expected [111, 112]. One study on the disposition of zidovudine (AZT) found that NTX had no significant effect on the area under the curve, maximal concentration or half-life of AZT [113]. In turn, another study suggested that NTX might potentiate the antiviral effects of AZT and a protease inhibitor, Indinavir, increasing their antiviral activity 2-3 fold [9]. A recent study suggests that NTX may inhibit the alcohol-mediated enhancement of HIV infection in T lymphocytes [114]. In addition, a large multi-center safety study of the use of NTX for alcoholism in 865 individuals, including patients with comorbid psychiatric illness and HIV, demonstrated that serious side effects in these populations were uncommon [115]. While this study was not randomized and was not intended to look at medication interactions, the findings are reassuring for patients with HIV disease. The proposed study will examine the question of clinically significant medication interactions through laboratory assessments and a systematic evaluation of adverse effects.

### **Addressing HIV provider's concern regarding provision of NTX for alcohol problems**

Physicians cite a number of barriers to providing NTX for the treatment of alcohol use disorders including lack of knowledge of the medication's safety and efficacy, time for patient management, and overall lack of involvement in alcoholism treatment [116-119]. The model proposed in the current study, alcohol treatment that is integrated into the HIV care setting, has potential to address some of these concerns. Integrated treatment for HIV and substance abuse disorders has been shown to help ameliorate some of the problems with access to care and sub-optimal treatment for both conditions [12, 120]. While integration of these services can be implemented at various levels including at that of the provider, the clinic, or the system, any successful integration will require support of providers based on treatment efficacy. The goal of the proposed study is to provide clinicians with data on the efficacy of VIVITROL in HIV-infected patients in order to reassure them about its tolerability and utility.

### **3. Research Plan:** Provide an orderly scientific description of the study design and research procedures as they directly affect the subjects.

#### **Overview**

The proposed study of HIV-infected patients with inadequate HAART adherence and heavy drinking, alcohol abuse and dependence will consist of a 24-week double-blind placebo-controlled randomized clinical trial, with an additional 6 months of follow-up, to evaluate the effect of treatment with VIVITROL versus placebo in conjunction with a counseling intervention on HIV outcomes. HIV outcomes will include: HAART medication adherence (specifically the proportion of patients achieving 95% or greater HAART adherence, viral mutations, HIV biologic markers, and alcohol-HAART hepatotoxicity. The counseling intervention is a "compound" therapy consisting of Medical Management (MM) counseling and Medication Coaching (MC). MM was developed for the NIAAA-funded COMBINE Study and consists of a series of brief interventions delivered by medically trained providers (physician or nurse) that has demonstrated efficacy when combined with NTX to reduce the frequency of heavy drinking [10]. MC is a counseling strategy which focuses on HAART medication adherence in substance abusing populations [11]. Of the total study population of 154 patients, 50 patients will be enrolled in the study at Yale and will be randomized to receive one of two treatment conditions: VIVITROL + MM/MC versus Placebo + MM/MC. MM/MC is intended to approximate the type of treatment that would be suitable for implementation by a trained individual (e.g. physician, nurse, nurse practitioner, physician assistant,) in a HIV primary care setting and approximates the counseling interventions that we have implemented in opioid dependent patients receiving buprenorphine treatment in primary care [122] and HIV primary care settings [100].

## **Participants**

### Sample size estimation

A total of 154 participants will be enrolled at the three participating clinics. The following assumptions were used to derive this sample size:

Proportion of Placebo+MM/MC participants achieving >95% adherence = 20%

Proportion of Vivitrol+MM/MC participants achieving >95% adherence = 40%

Power=72%

Alpha level=0.05

Participants at the Nathan Smith Clinic will be 50 HIV-infected men and women who report heavy drinking, alcohol abuse or dependence. Referrals will come from within the Nathan Smith Clinic site, via local HIV care sites, website advertisements, local papers, community postings, community physicians, other patients, local mental health centers, local hospitals, and substance abuse treatment facilities.

***Inclusion criteria:*** Each subject must:

1. Be HIV-infected.
2. Currently be prescribed HAART medication.
3. Report less than 95% adherence to their HAART medication.
4. Report heavy drinking 4 or more times in the past 4 weeks, or meet current criteria for alcohol abuse or dependence. Heavy drinking is defined as 4 or more drinks for women and 5 or more drinks for men on one occasion.
5. Be at least 18 years old.
6. Be able to understand English and provide informed consent.

***Exclusion criteria:*** No subject may:

1. Be psychotic or severely psychiatrically disabled.
2. Be currently enrolled in formal treatment for alcohol (excluding self-help, e.g. Alcoholics Anonymous)
3. Have medical conditions that would preclude completing or be of harm during the course of the study.
4. Have laboratory or clinical evidence of significant liver dysfunction (alanine aminotransferase (ALT) or aspartate aminotransferase (AST) greater than 5 times the upper limit of the normal range) or cirrhosis with a Child-Pugh classification greater than A or B.
5. Have a known contraindication to NTX therapy (e.g. requiring opioid medication for pain).
6. Be pregnant, nursing or unable to use an effective method of birth control (women).
7. Patients with a positive urine opioid screen result
8. Known hypersensitivity to naltrexone, PLG (polylactide-co-glycolide, carboxymethylcellulose, or any other components of the diluent

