clinical settings, and the likelihood of underestimation of adherence due to patients' "pocket dosing" their medication or removing more than one dose for each bottle opening, lead us to choose the other three methods in order to measure adherence [130].

We anticipate that a number of HIV-infected patients with heavy drinking may not be prescribed HAART medications due to their providers' concerns about poor medication adherence. While such patients do not meet the second eligibility criterion, we will encourage interested patients to discuss the possibility of resuming HAART with their HIV providers, such that they could be considered for enrollment at a later date. In addition, in an effort to include this target sub-population without mandating the usual 90 days of HAART-adherence data, we will determine their baseline adherence after 30 days; patients will be invited to present for an eligibility assessment one month after their first HAART prescription. We will use a simple 30-day pill count to calculate their baseline adherence.

**The Morisky scale** is a commonly used, validated, 4-item self-reported adherence measure that has been shown to be predictive of medication adherence. It includes two items that measure intentional medication non-adherence.

**Alcohol Use** will be assessed using the Time-Line Follow Back Interview (TLFB) [131] which will obtain the quantity/frequency of alcohol consumed for each day in the past month (baseline) and since the prior visit. TLFB has good test-retest reliability and good validity [131]. In addition, in order to better determine the "category" of drinking behavior of a subject at baseline, we will use the Alcohol Use Disorders Identification Test (AUDIT) [26], a valid instrument for categorizing alcohol consumption.

**The Obsessive-Compulsive Drinking Scale (OCDS)** is a 14-item, self-administered questionnaire for characterizing and quantifying the obsessive and compulsive cognitive aspects of craving and heavy (alcoholic) drinking, such as drinking-related thought, urges to drink, and the ability to resist those thoughts and urges.

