**Table 1: Summary of Study Assessments**

	Wk -1	Wk 0	Wk 2	Wk4	Wk 6	Wk 8	Wk 12	Wk 16	Wk 20	Wk 24	Mn 9	Mn 12
History (demographic and clinical data) and physical exam	X											
Chart review for historical genotypic information	X											
SCID	X											
AUDIT	X											
OPRM1 genotyping	X											
Hepatitis B and C serologies	X											
Urine pregnancy test	X			X		X	X	X	X			
Liver enzymes (AST, ALT, GGT)	X			X		X	X	X	X	X	X	X
CBC, chemistries	X			X		X	X	X	X	X	X	X
CD4 count and HIV RNA	X			X		X	X	X	X	X	X	X
Standard HIV drug resistance testing and ultra-deep sequencing	X			X		X	X	X	X	X	X	X
Pharmacy fill/refill data for HAART adherence	X						X			X	X	X
Urine Drug Screen (for THC, opioids, coke, benzos at baseline; for opioids at other timepoints prior to VIVITROL injection)		X		X		X	X	X	X			
ACTG HAART medication adherence		X	X	X	X	X	X	X	X	X	X	X
HAART Persistence Questions		X	X	X	X	X	X	X	X	X	X	X
Visual Analog Scale (10cm): Adherence		X	X	X	X	X	X	X	X	X	X	X
Morisky 4-item Adherence Scale		X	X	X	X	X	X	X	X	X	X	X
Time-Line Follow Back (TLFB) for alcohol consumption	X		X	X	X	X	X	X	X	X	X	X
Alcohol Craving analog scale		X		X		X	X	X	X	X	X	X
OCDS		X		X		X	X	X	X	X	X	X
Substance Use Survey		X		X		X	X	X	X	X	X	X
PEth testing		X				X			X			X
Breathalyzer test (BAC)		X	X	X	X	X	X	X	X	X		
Sexual risk behaviors		X		X		X	X	X	X	X	X	X
SF-12		X		X		X	X	X	X	X	X	X
TSR				X		X	X	X	X	X	X	X
ASI-Lite		X								X		X
BSI		X								X		X
SIP		X								X		X
Brief Pain Inventory (+ Supplement)		X								X		X
SAFTEE		X	X	X	X	X	X	X	X	X		
VIVITROL injection		X		X		X	X	X	X			
Counseling Session		X	X	X	X	X	X	X	X			
Assessment compensation	X			X		X	X	X	X	X	X	X
Patient satisfaction survey						X			X			

4. **Statistical Considerations:** Describe the statistical analyses that support the study design.

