HAART medication adherence, specifically focusing on the proportion of patients achieving 95% or greater HAART adherence (See justification for this threshold in Section B.7.), will be evaluated using pharmacy fill/refill data on a monthly basis and self-report. For each month of the 24-week treatment period, and the 9 and 12 month follow-up periods, we will calculate the number of days of HAART medication adherence. Because HAART, the simultaneous use of  $\geq 3$  antiretroviral medications, is considered the standard of care for HIV-infected individuals, patients will be classified as adherent when their regimen medication possession ratio (MPR) (calculated as the days' supply of medication divided by the number of days between the first fill and the last refill [84]) is  $> 0.95$ , signifying greater than 95% adherence. We will also capture the MPR of all anti-retroviral medications. In prior work, we have shown that over a one year study period in VACS, the HAART MPR was 70% compared to 77% of any anti-retroviral total (Kim et al, unpublished). For patients who are on HAART but less than 95% adherent, we will determine what proportion of this group achieved greater than 95% adherence.

For primary outcome analysis, both aggregate and stratified analyses will be carried out to compare the proportion of participants in each of the two groups who achieve  $\geq 95\%$  adherence during the last four months of observation.

The probability of achieving the primary outcome will be modeled using logistic regression analysis. An unadjusted model (treatment) and models that include covariate adjustment (treatment plus other predictor variables eg depression, race, opiate receptor genetics, CD4 level, viral load level) will be executed.

In addition and, as appropriate, linear mixed effects models will be used to assess changes in adherence over the six months of observation. Models will include a fixed effect for treatment status, time as a continuous variable representing the month of observation, and the interaction between treatment and time in order to assess difference in slopes of change by treatment status. Random effects will be included to account for intra-subject correlation of repeated measures. Additional factors that may impact rate of change in adherence include time-varying covariates such as CD4 and viral load. Model fit will be assessed with analysis of residuals and other standard methods for assessing goodness-of-fit [136].

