There are multiple strategies to measure adherence (See Sections B.8. and B.9.). Based on strong evidence in support of this strategy [72, 88, 89], we have chosen to examine the percentage of patients, using pharmacy fill-refill data, who achieve 95% or better adherence to their HAART treatment as our primary outcome measure of adherence [60, 117]. We will also examine adherence using self-report data collected using AIDS Clinical Trials Group (ACTG) assessment. Patients will be classified as meeting the criteria for greater than 95% adherence if they are adherent 29-30 days out of the past 30 days. We will use the Chi-Square test to compare the proportion of patients in each randomization group meeting these criteria during each month of the study. The t-test will be used to compare HAART medication adherence between the two treatment conditions based on self-report.

**Specific Aim 2:** To compare the efficacy of VIVITROL +MM/MC versus placebo +MM/MC in reducing days of heavy drinking.

**Hypothesis 2:** VIVITROL +MM/MC counseling will lead to greater reductions in the number of days of heavy drinking when compared to placebo + MM/MC.

We plan to use a standard alcohol consumption outcome, the number of days of heavy drinking (4 or more drinks per drinking occasion for women and 5 or more drinks per drinking occasion for men) in the past 30 days. This measurement was one of the outcomes

APPROVED BY THE YALE UNIVERSITY IRB 10/11/2018 VALID THROUGH 10/13/2019  

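### Entry is by self-reported adherence below 95% but the primary endpoint is 95% by pharmacy refill, so patients already at the endpoint on its own measure can be enrolled and counted as achieving it

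*Combined protocol and SAP*

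**What the plan says.** **Entry.** Criterion 3, in Section V (Participants) and again in Section VII item 3, requires that the patient "Report less than 95% adherence to their HAART medication". Neither list names an instrument, a look-back period or an MPR threshold.

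**Endpoint.** Under Statistical analyses, Specific Aim 1, the plan takes the percentage of patients, "using pharmacy fill-refill data, who achieve 95% or better adherence to their HAART treatment as our primary outcome measure of adherence". Patients are classified by regimen MPR, and the arms are compared on "adherence during the last four months of observation".

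**How the measures relate.** The Background discussion of pharmacy refill says that MPR "represents the maximum possible adherence that a patient can attain over a defined refill period". It adds that refilling is a precondition for adherence but does not guarantee it.

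**Baseline data.** Table 1 schedules "Pharmacy fill/refill data for HAART adherence" at week -1. The self-report adherence instruments start at week 0, the visit of the first injection. For patients newly started or restarted on HAART, Baseline and in-treatment assessments says that, "without mandating the usual 90 days of HAART-adherence data, we will determine their baseline adherence after 30 days", using a pill count. Neither the 90 days nor the pill count appears in the eligibility lists, and Table 1 has no pill-count row.

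**Analysis.** The Aim 1 text adds: "For patients who are on HAART but less than 95% adherent, we will determine what proportion of this group achieved greater than 95% adherence". It names no baseline measure and does not make this group the primary analysis set. Randomisation is stratified by clinic and alcohol abuse/dependence. The example covariates for the logistic model do not include baseline MPR.

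**The concern.** The Statement of Purpose aims the trial at patients with inadequate adherence, and the endpoint is worded as reaching 95%. Entry and endpoint use different measures, and the protocol says the endpoint measure can only overstate adherence. A patient who collects every fill on time but misses doses can truthfully report less than 95% while holding an MPR at or above it. That patient is eligible and already meets the endpoint at entry, so can only keep or lose it.

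Two things are at stake. A responder count that mixes patients who improved with patients who merely stayed where they were is hard to interpret. And if treatment has little effect on the second group, they raise both arms' rates alike and shrink the difference the trial was sized to detect. Planned power is only 72%, so there is little margin.

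**Working it through.** **Inputs from the plan (Sample size estimation):** placebo 20%, active 40%, alpha 0.05, power 72%, total 154. Taken as 77 per arm (participants are told they have a 50% chance of active drug). Sidedness is not stated; two-sided is assumed.

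**Step 1. Reproduce the stated power.** Two-proportion test with continuity correction:

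power = Φ{ (d − 1/n − 1.96·s0) / s1 }, where d is the difference in rates, p̄ their mean, s0 = √[2p̄(1−p̄)/n] and s1 = √[(p1(1−p1) + p2(1−p2))/n].

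With n = 77, p1 = 0.20, p2 = 0.40: d = 0.20, 1/n = 0.0130, s0 = 0.0739, s1 = 0.0721. Then (0.20 − 0.0130 − 0.1448)/0.0721 = 0.586, and Φ(0.586) = 72.1%. The stated 72% is reproduced. Without the correction it would be 77.8%.

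**Step 2. Add patients already at the endpoint.** Let f be the share of enrolled patients with baseline MPR of 95% or more. The documents do not give f; 10%, 20% and 30% are assumed. Let r be the probability that such a patient is still at 95% in the outcome window. Each arm's rate is then (1−f)·p + f·r, with p = 0.20 or 0.40 for the remaining patients.

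*Scenario A: r = 0.8 in both arms, so no treatment effect on retention.* The difference is 20 × (1−f) points.

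| f | placebo | active | difference | power |
|---|---|---|---|---|
| 10% | 0.9×0.20 + 0.1×0.8 = 26% | 0.9×0.40 + 0.1×0.8 = 44% | 18 points | 58.6% |
| 20% | 32% | 48% | 16 points | 46.0% |
| 30% | 38% | 52% | 14 points | 35.2% |

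Varying r from 0.6 to 1.0, equal in both arms, gives 58–60%, 45–48% and 35–36%.

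*Scenario B: r = 0.6 on placebo and 0.8 on active, so treatment helps retention.* The difference stays at 20 points; power falls only because both rates move towards 50%.

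| f | placebo | active | power |
|---|---|---|---|
| 10% | 0.9×0.20 + 0.1×0.6 = 24% | 0.9×0.40 + 0.1×0.8 = 44% | 69% |
| 20% | 28% | 48% | 67% |
| 30% | 32% | 52% | 66% |

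*Scenario C: the 20% and 40% already include such patients.* Power remains 72%. What changes is the meaning of the rates. With f = 10% and everyone retained, 0.10/0.20 = half of the expected placebo responders and 0.10/0.40 = a quarter of the expected active-arm responders met the endpoint at entry.

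**Step 3. Restricting the analysis to baseline MPR below 95%.** At f = 10%, 20% and 30% this leaves 77×(1−f) = 69, 62 and 54 per arm. At 20% versus 40%, power is 67%, 61% and 54%. That is better than all randomised under scenario A and worse under scenario B.

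**The case against.** The strongest reply is that an objective screen was probably intended. Refill data are the only adherence measure Table 1 schedules at the screening visit, and the remark about a usual 90 days of adherence data occurs in a discussion of eligibility. Self-report may be the pre-screen, with refill history or a pill count confirming entry. That is a fair reading, and sites may work that way. It remains unwritten: neither eligibility list requires a baseline MPR below 95%.

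A second reply concerns size, and it largely stands. The sample-size section attaches 20% and 40% to the participants of each arm, not to those starting below 95% on refill, so scenario C is open. The endpoint covers the last four months of observation, so treatment could act by preventing loss of adherence, as in scenario B. Nothing shows that near-perfect refilling is common in this population. The only refill figure given is a HAART MPR of 70% over one year in the investigators' earlier cohort. The Background shows that discordance is possible, not how frequent it is.

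A reader might infer two stronger claims. One is that the comparison between arms is biased. It is not: randomisation balances these patients in expectation. The other is that the trial is shown to have much less than 72% power. The documents do not support that, because it needs an undocumented f, planning rates confined to the other patients, and no treatment effect on retention.

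**Conclusion.** The mismatch is in the text and should be corrected. Entry is by report, the endpoint is by refill MPR, and baseline MPR is not an entry condition, a stratification factor or a listed covariate. The certain consequence is one of interpretation: the responder count can include patients who met the endpoint when they enrolled. Loss of power is possible but cannot be sized from the documents. For 10% to 30% of such patients the illustrations run from about 59–35% (scenario A), through 69–66% (scenario B), to no change from 72% (scenario C). The planned look at patients below 95% mitigates this only in part, because its baseline measure is not named.

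**What to change.** **Eligibility.** In both lists, state that entry requires regimen refill MPR below 95% over a defined look-back before week -1, for example the 90 days the protocol calls usual. Use the refill data scheduled at that visit, and keep self-report as a pre-screen. Say how MPR is computed when the window holds too few fills: it is defined from first fill to last refill, so long-supply prescriptions could leave it undefined. Write the 30-day pill-count exception into the criteria and Table 1.

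**Participants already randomised.** Keep the intention-to-treat primary analysis and add baseline (pre-randomisation) MPR as a covariate in the logistic model. Name refill MPR as the baseline measure in the sentence on patients below 95%, and pre-specify that comparison as a supporting analysis. Making the subset primary would depart from the intention-to-treat plan, and Step 3 shows its power could be better or worse.

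**Cost.** An amendment to one criterion and Table 1. The refill pull is already scheduled, but its look-back must be specified and may need to be longer than sites now collect. Some self-reported non-adherers with full refill records become ineligible, so screening will take longer.
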